10.2 Treatment schedule and design

Upon completion of the required assessments in the screening phase and fulfillment of the eligibility criteria, eligible patients will be included and will enter in the treatment phase.

Patients with high tumor load may receive a pre-phase treatment of COP described below. The pre-phase therapy should be started after inclusion and after samples for MRD analysis.

Chemotherapy regimen	Dose	D1	D2	D3	D4	D5
Prednisolone	80 mg/m ²	X	X	X	X	X
Cyclophosphamide	750 mg/m ²	X				
Vincristine	1.4 mg/m ²	X				

10.2.1 *Induction treatment: GA-DHAP*

Patients will receive 4 cycles of GA-DHAP every 21 days.

*In case of toxicities related to cisplatin or according to the local investigator choice, carboplatinum AUC = 5 could be used instead of cisplatinum.

G-CSF administration is required during treatment cycles and stem cell collections.

10.2.1.1 Cycle 1

- Patients will receive their first Obinutuzumab infusion (1000 mg) on Day 1 (Cycle 1 Day 1) along with standard premedication. During Cycle 1, Obinutuzumab will also be administered on Days 8 and 15.
- Patients will be monitored for signs of acute tumor lysis syndrome (TLS)
- For patients treated with pre-phase, Cycle 1 has to be started 1 week after the end of the COP
- The products doses should be capped at 2m²

Chemotherapy regimen	Dose	D1	D2	D3	D4	D8	D15
Dexamethasone	40mg	X	X	X	X		
GA-101 IV	1000mg	X				X	X
Aracytine IV (every 12 hours)	2 g/m ²	X X					
Cisplatinum* IV	100 mg/m ²	X					

10.2.1.2 Cycle 2 to 4 one cycle every 21 days

Chemotherapy regimen	Dose	D1	D2	D3	D4
Dexamethasone	40mg	X	X	X	X
GA-101 IV	1000mg	X			
Aracytine IV (every 12 hours)	2 g/m ²	X X			
Cisplatin* IV	100 mg/m ²	X			

10.2.1.3 Peripheral stem cell collection

Collection of peripheral blood stem cell progenitors will be organized after cycle 3 at the time of hematological recovery with G-CSF support. In case of failure to collect a sufficient number of CD34+ cells at this phase, a second attempt will be performed after the fourth cycle. CD34+ cells will be quantified to evaluate the graft and methods of determination will be performed according to each center policy and reported.

The target dose of collected CD34+ cells is 3×10^6 cells/kg.

Leukapheresis will be performed according to current recommended practice. Procedures of harvest, freezing and storage will be performed according to each center policy.

In case of failure to harvest a sufficient number of CD34+ after these two attempts, the patient will be treated according to physician decision.

10.2.2 Conditioning regimen and ASCT: GA-BEAM

All patients in complete remission, complete remission unconfirmed, partial remission or stable disease (according to Cheson 99) after induction treatment will be transplant.

Autologous transplantation will be performed in hematopoietic stem cell transplantation authorized centers.

The conditioning regimen has to start 4 to 8 weeks after D1 C4.

Chemotherapy regimen GA-BEAM	Dose	D-8	D-7	D-6	D-5	D-4	D-3	D-2	D-1	D0	
GA101	1000mg	X									G R A F T
BCNU	300 mg/m ²		X								
Etoposide	400 mg/m ²			X	X	X	X				
Aracytine (Cl)	400 mg/m ²			X	X	X	X				
Melphalan	140 mg/m ²							X			

G-CSF administration is required from day 7 of ASCT.

10.2.3 **Maintenance: Obinutuzumab**

All the patients in complete remission, unconfirmed complete remission, partial remission or stable disease (according to the Cheson 99 criteria) after ASCT and whatever the result of the MRD analysis (negative or positive) will receive a maintenance treatment for 3 years.

The maintenance treatment will start between 2 to 3 months after D1 of ASCT.

The patient will be treated with one injection of Obinutuzumab every 2 months for 3 years.

Treatment	Dose	D1 every 2 months
GA-101 IV	1000mg	X

The patients with an informative MRD at baseline on bone marrow and/or blood (MRD done before starting induction, with characterized tumoral clone) will continue with 3 additional years of maintenance in which the patients will receive Obinutuzumab according to their MRD status, the so-called "on-demand" maintenance.

During the "on-demand" maintenance, the patients with a negative MRD status will not receive Obinutuzumab while the patients with a positive MRD status will be treated with Obinutuzumab as follows: the therapeutic scheme will be one Obinutuzumab injection at D1, 8 and 15 for cycle 1 and then every month. The Obinutuzumab injections will be continued until the patients reach MRD negativity plus one additional injection after the last MRD negative control. The patients, whom the MRD becomes positive, will restart the obinutuzumab injections.

Treatment	Dose	1 st month			Every month
		D1	D8	D15	D1
GA-101 IV	1000mg	X	X	X	X

This scheme has to be used several times until clinical progression, in case of unacceptable toxicity or until of the 3-years period ends, whichever comes first.

The patients who prematurely stop the study treatment or the patients with disease progression will be followed until the end of the trial.

10.3 Dose adjustments

10.3.1 **Hematological toxicity**

10.3.1.1 **Management of hematological toxicity in patients receiving DHAP**

If neutrophils $<1 \times 10^9/l$ or thrombocytes $<20 \times 10^9/l$ postpone 1 week.

Based on the potential toxicity, a sufficient hydration (2-3 l/m² and day) and regular ENR examinations during the course of Cisplatin containing induction therapy is mandatory.

10.3.1.2 Management of hematological toxicity in patients receiving GA101

10.3.1.2.1 **Neutropenia**

Cases of Grade 3 or 4 neutropenia, including febrile neutropenia, have been reported with GA101 administration. Grade 3 or 4 neutropenia has predominantly been observed in patients with CLL. Patients who experience Grade 3 or 4 neutropenia should be monitored until neutrophil values return to at least Grade 2. Use of granulocyte colony-stimulating factors (G-CSF) has been found to result in a rapid normalization of neutrophils, similar to what has been observed in patients treated with rituximab. The use of G-CSF is allowed for treatment of neutropenia in this study. Primary prophylaxis with G-CSF is recommended according to the American Society of Clinical Oncology (ASCO), EORTC, and European Society for Medical Oncology (ESMO) guidelines, namely for patients who are \geq 60 years old and/or with co-morbidities (Lyman et al. 2004). The use of G-CSF is mandatory in Cycle 1 for all patients.

10.3.1.2.2 **Thrombocytopenia**

Severe and life threatening thrombocytopenia including acute thrombocytopenia (occurring within 24 hours after the infusion) has been observed during treatment with GA101. Fatal haemorrhagic events have also been reported in patients treated with GA101. It seems that the first cycle is the greatest risk of haemorrhage in GA101-treated patients. A clear relationship between thrombocytopenia and haemorrhagic events has not been established. Patients treated with concomitant medication, which could possibly worsen thrombocytopenia related events such as platelet inhibitors and anticoagulants, may be at greater risk of bleeding. Patients should be closely monitored for thrombocytopenia, especially during the first cycle; regular laboratory tests should be performed until the event resolves, and dose delays should be considered in case of severe or life-threatening thrombocytopenia. Transfusion of blood products (i.e. platelet transfusion) according to institutional practice is at the discretion of the treating physician.

10.3.1.2.3 **GA101 dose adjustments**

There will be no dose reductions for GA101 (1000 mg). During Cycle 1, the Day 8 and D15 doses of GA101 may be administered whatever the neutrophil count if there is no evidence of infection or bleeding and if platelet count is $>50 \times 10^9 / L$.

If the platelet count is $<50 \times 10^9 / L$, GA101 will not be administered and the platelet count will be closely monitored and platelet transfusion will be performed to maintain a platelet count $>20 \times 10^9 / L$.

If the patient presents an active infection of any grade at day 8 or at day 15 of the first cycle of induction treatment, GA101 will not be administered.

10.3.2 **Renal toxicity**

If $>50\%$ decrease of creatinin clearance, cisplatin will be stopped or replaced by carboplatinum AUC = 5

10.3.3 **Neurotoxicity**

In case of neurotoxicity such as peripheral neuropathy, severe constipation/paralytic ileus, ototoxicity: cisplatin should be reduced by 50% or stopped according to the discretion of the treating physician.

Carboplatinum AUC = 5 could be used instead of cisplatin

10.3.4 **Potential risk of Progressive Multifocal Leukoencephalopathy (PML)**

The therapy with anti-CD 20 antibodies (obinutuzumab) should be discontinued during the investigations of a potential PML and permanently stopped if the diagnosis of PML is confirmed. Discontinuation or reduction of any concomitant chemotherapy or immunosuppressive therapy should also be considered. The patient should be referred to a neurologist for the adequate monitoring and treatment of PML.

10.3.5 **Other toxicities**

Other toxicities will be managed according to local practice and guidelines of chemotherapy induced toxicities

10.4 Concomitant treatment

Any patient treatments taken 8 days prior to study treatment, at any time during the study and up to 28 days after the end of the study treatment will be considered as concomitant treatments.

10.4.1 **Prohibited therapies**

The following concomitant treatments are not permitted during this study treatment:

- Systemic anticancer agents other than study drugs.
- Other investigational therapies or devices.
- Concomitant radiotherapy.

If a patient's clinical status requires administration of a prohibited concomitant medication or treatment, then administration of study drugs should be stopped, and the patient will be withdrawn from the study treatment.

The change in clinical status mandating the use of the medication in question must be reported as the reason for study drug discontinuation.

10.4.2 **Restricted/allowed therapies**

Patients will be instructed not to take any additional medications (including over-the-counter products) during the course of the study without prior consultation with the investigator. At each visit, the investigator will ask the patient about any new medications he/she is or has taken after the start of the study drug.

All therapies necessary for the patient management are permitted besides other antineoplastic agents for lymphoma. The use of antibiotics and other supportive therapies is in the discretion of the treating physician.

Administration of Granulocyte colony-stimulating factor is mandatory after each GA101-DHAP cycle and recommended after autologous stem cell transplant (see section 10.2).

Platelet and red blood cell transfusions are permitted, as necessary.

10.5 Prophylactic measures

10.5.1 **Infusion-Related Reactions related to Obinutuzumab**

The most frequently observed adverse drug reactions (ADR) in patients receiving Obinuzumab were IRR; these occurred predominantly during the first infusion. The incidence and severity of infusion related symptoms decreased substantially with subsequent infusion.

See also section 10.1.5. *Administration* for the management of IRR

During induction treatment, dexamethasone should be administrated before the infusion of Obinutuzumab

If a patient experiences an IRR during the prior infusion, he should receive 100mg prednisolone or equivalent.

If a patient does not experience an IRR (grade ≥ 1) during the first infusion, the premedication for the infusions of maintenance can be omitted.

The first Obinutuzumab infusion should be administered to patient after premedication with oral analgesic/anti pyretic (e.g. 1000mg) and anti-histaminic drug (e.g. 50 mg diphenhydramine)

Grade 4 (life-threatening)	Stop infusion and discontinue therapy.
Grade 3 (severe)	Temporarily interrupt infusion and treat symptoms. Upon resolution of symptoms, restart infusion at no more than half the previous rate (the rate being used at the time that the IRR occurred) and, if patient does not experience any IRR symptoms, infusion rate escalation may resume at the increments and intervals as appropriate for the treatment dose
Grade 1-2 (mild and moderate)	Reduce infusion rate and treat symptoms. Upon resolution of symptoms, continue infusion and, if patient does not experience any IRR symptoms, infusion rate escalation may resume at the increments and intervals as appropriate for the treatment dose

10.5.2 ***Tumor Lysis Syndrome***

Patients who are considered to be a risk of TLS (e.g. patients with a high tumor burden or a high circulating lymphocyte count) should receive adequate tumor lysis prophylaxis with allopurinol (or adequate alternative) and hydration starting 12-24 hours prior to the infusion of Obinutuzumab.

10.5.3 ***Infection***

Obinutuzumab should not be administrated in the presence of an active infection.

Prophylaxis of infections is required for all patients during all the study treatment, in the discretion of the treating physician.

Physicians should exercise caution when considering the use of GA101 in patients with a history of recurring or chronic infections or with underlying conditions that may predispose patients to infections. Advice should be given to patients to minimize the risks of acquiring infections from endogenous sources e.g. oral hygiene, avoidance of constipation etc. Signs and/or symptoms of infection should result in prompt evaluation and appropriate samples for bacteriological investigation prior to starting antibiotic or other treatment by the treating physician.

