	
 Viral infection with hepatitis B virus (HBV) defined as hepatitis B surface antigen (HBsAg) positive and/or Hepatitis B core antibody (anti-HBc) positive Note: Patients who are immune due to hepatitis B vaccination or natural infection (HBs Ag and anti-HBc negative, anti-HBs positive) are eligible. But the patients who are immune due to hepatitis B natural infection should consult liver disease experts before start of treatment and should be monitored and managed following local medical standards to prevent hepatitis reactivation Prior history of Progressive Multifocal Leukoencephalopathy (PML) Vaccination with a live vaccine a minimum of 28 days prior to inclusion (Prolonged B cell depletion) History of severe allergic or anaphylactic reactions to humanized or murine monoclonal antibodies. Known sensitivity or allergy to murine products Psychiatric illness or condition which could interfere with their ability to understand the requirements of the study. Person deprived of his/her liberty by a judicial or administrative decision Person hospitalized without consent Adult person under legal protection
Study design	
Induction
 
GA-BEAM + ASCT → GA101 every 2 months
 
3w 3w 3w 4w/8w
 
● GA101
 
↓ D1 DHAP (or C according to local investigator choice)
 
Maintenance during 3 years
 
GA101 every 2 months
 
Maintenance "on-demand" during 3 years
 
No treatment
 
MRD
 
GA101 every month
 
MRD

Study treatment	
Patients will receive 4 cycles of GA-DHAP* every 21 days followed by ASCT using a GA-BEAM conditioning regimen plus a Obinutuzumab maintenance for 3 years then a Obinutuzumab maintenance on demand according to MRD status. Stem cells will be collected after cycle 3 and/or 4 of GA-DHAP*.
 
Patients with high tumor load may receive a pre-phase treatment of COP. The pre-phase therapy should be started after inclusion and after samples for MRD analysis and cycle 1 of GA-DHAP has to be started 1 week after the end of the COP.
 
In this trial, obinutuzumab is considered as investigational medical product (IMP).
 
Cycle 1 :
 
 Patients will receive their first obinutuzumab infusion (1000 mg) on Day 1 (Cycle 1 Day 1) along with standard premedication. During Cycle 1, obinutuzumab will also be administered on Days 8 and 15.

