- Following obinutuzumab infusion, patients will receive DHAP chemotherapy as per standard administration procedures, along with standard premedications.
- Patients will be monitored for signs of acute TLS

Chemotherapy regimen	Dose	D1	D2	D3	D4	D8	D15
Dexamethasone	40mg	X	X	X	X		
GA-101 IV	1000mg	X				X	X
Aracytine IV	2 g/m ² /12h	XX					
Cisplatinum* IV	100 mg/m ²	X					

Cycle 2 to 4: one cycle every 21 days

Chemotherapy regimen	Dose	D1	D2	D3	D4
Dexamethasone	40mg	X	X	X	X
GA-101 IV	1000mg	X			
Aracytine IV	2 g/m ² /12h	XX			
Cisplatinum* IV	100 mg/m ²	X			

G-CSF administration is required during treatment cycles, stem cell collection and ASCT.

*In case of toxicities related to cisplatinum or according to the local investigator choice, Carboplatinum AUC = 5 could be used instead of cisplatinum

ASCT :

GA-BEAM: 4 to 8 weeks after D1 C4

Chemotherapy Regimen GA-BEAM	Dose	D-8	D-7	D-6	D-5	D-4	D-3	D-2	D-1	D0
GA-101 IV	1000mg	X								G
BCNU	300 mg/m ²		X							R
Etoposide	400 mg/m ²			X	X	X	X			A
Aracytine (Cl)	400 mg/m ²			X	X	X	X			F
Melphalan	140 mg/m ²							X		T

Maintenance:

Obinutuzumab maintenance: start between 2 to 3 months after D1 of ASCT. All patients in complete remission, complete remission unconfirmed, partial remission or stable disease (according to Cheson 99) will receive one injection of Obinutuzumab

every 2 months for 3 years.

Treatment	Dose	D1 every 2 months
GA-101 IV	1000mg	X

When the MRD is informative at baseline in bone marrow and/or blood (prior to any treatment, before starting induction), this period will be followed by a maintenance “on-demand” for 3 years only for MRD positive patients at the end of the first 3 years of maintenance, MRD negative patients will stop obinutuzumab infusion. The therapeutic scheme will be one injection every month of Obinutuzumab (one injection at D1, 8 and 15 for the first month and then one time every month) until MRD negativity plus one additional injection after the last MRD negative control. MRD analyses will be continued for all patients with informative MRD and every patient once again with a positive MRD will restart Obinutuzumab maintenance.

treatment	Dose	1 st month			Every month
		D1	D8	D15	D1
GA-101 IV	1000mg	X	X	X	X

This scheme has to be used several times until clinical progression, toxicities or until end of the 3-years period, whichever comes first.

Patients who withdraw from the study treatment or patients who progress will be followed until the end of the trial.

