Dilution preparation:

Using a 250-mL infusion bag containing 0.9% sodium chloride, withdraw and discard 40 ml of the sodium chloride.

Withdraw 40 ml of Obinutuzumab from a single glass vial and inject into the infusion bag (discard any unused portion of Obinutuzumab left in the vial). Gently invert the infusion bag to mix the solution; do not shake.

10.1.5 **Obinutuzumab: Administration**

See also section 10.5.1. *Infusion-Related Reactions related to Obinutuzumab* and section 10.5.2 *Tumor Lysis Syndrom*

Infusion rates of Obinutuzumab will be managed as follows:

Administration of First and Subsequent Infusions of GA101

First Infusion (Day 1 of Cycle 1)	Subsequent Infusions

 • Begin infusion at an initial rate of 50 mg/hour. • If no infusion-related or hypersensitivity reaction occurs, increase the infusion rate in 50-mg/hour increments every 30 minutes, to a maximum of 400 mg/hour. • If a reaction develops, stop or slow the infusion. Administer medications and supportive care in accordance with institutional guidelines. If reaction has resolved, resume the infusion at a 50% reduction in rate (i.e., 50% of rate being used at the time that the reaction occurred). 	
 • If the patient experienced an infusion-related or hypersensitivity reaction during the prior infusion, use full premedication including 100 mg prednisone/prednisolone (until no further IRR occurs), begin infusion at an initial rate of 50 mg/hour and follow instructions for first infusion. • If the patient tolerated the prior infusion well (defined by an absence of Grade 2 reactions during a final infusion rate of ≥ 100 mg/hour), begin infusion at a rate of 100 mg/hour. • If no reaction occurs, increase the infusion rate in 100-mg/hour increments every 30 minutes, to a maximum of 400 mg/hour. • If a reaction develops, stop or slow the infusion. Administer medications and supportive care in accordance with institutional guidelines. If reaction has resolved, resume the infusion at a 50% reduction in rate (i.e., 50% of rate being used at the time that the reaction occurred).

In all parts of the study, Obinutuzumab must be administered in a clinical (inpatient or outpatient) setting. Full emergency resuscitation facilities should be immediately available and patients should be under close supervision of the investigator at all times.

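### Steroid premedication in induction is stated in unreconciled places: the order on cycle 1 day 1 conflicts, and cover for the day 8 and day 15 infusions is unclear

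*Protocol*

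**What the plan says.** Four places in the protocol bear on steroid cover for obinutuzumab in induction.

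- **Section 10.5.1 (infusion-related reactions):** "During induction treatment, dexamethasone should be administrated before the infusion of Obinutuzumab". No cycle or day is excepted and no dose is given. For the first infusion it adds an analgesic/antipyretic and an antihistamine: "The first Obinutuzumab infusion should be administered to patient after premedication with oral analgesic/anti pyretic". After a reaction: "If a patient experiences an IRR during the prior infusion, he should receive 100mg prednisolone or equivalent". It allows premedication to be dropped only for maintenance infusions, and only if the first infusion caused no reaction.
- **Section 10.2.1.1 and the synopsis table for cycle 1:** the antibody is given three times ("During Cycle 1, Obinutuzumab will also be administered on Days 8 and 15"), while the steroid row reads "Dexamethasone 40mg X X X X", which fills days 1 to 4. The day 8 and day 15 cells of that row are empty. SAP Appendix A, Table 7.6-2, repeats the layout.
- **Section 10.1.5 (administration):** for subsequent infusions it names a steroid in one circumstance, a reaction at the prior infusion: "use full premedication including 100 mg prednisone/prednisolone (until no further IRR occurs".
- **Synopsis, Study treatment, Cycle 1:** "Patients will receive their first obinutuzumab infusion (1000 mg) on Day 1 (Cycle 1 Day 1) along with standard premedication", and then "Following obinutuzumab infusion, patients will receive DHAP chemotherapy as per standard administration procedures, along with standard premedications". Section 10.2.1.1 does not carry the second sentence and gives no order.

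**The concern.** The only dexamethasone in the schedules is the DHAP component. A site that works from the synopsis could give it after the first antibody infusion, and a site that works from section 10.5.1 would give it before. For days 8 and 15, a site that works from the tables and section 10.1.5 could give no steroid to a patient without a prior reaction. A site that works from section 10.5.1 would give dexamethasone, at a dose that this section does not state.

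The protocol itself presents dexamethasone as a measure against infusion reactions and says that these come mainly at the first infusion, which is where the order conflict lies. Grade 4 reactions are an adverse event of special interest (section 14.5). A rate of 10% or more in induction leads to an IDMC meeting (section 12), and a single grade 4 event ends therapy (section 10.5.1). Stopping therapy in turn moves the primary marrow assessment to the time of discontinuation. Tolerability at induction is a secondary objective. In a single-arm trial, no concurrent control would separate a difference in steroid practice from an effect of the drug.

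**Working it through.** **Number of induction infusions.** Cycle 1 has 3 (days 1, 8, 15) and cycles 2 to 4 have 1 each: 3 + 1 + 1 + 1 = 6. At 1000 mg each, 6 × 1000 = 6000 mg. This reproduces the expected induction total in SAP section 5.9.2.

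**Steroid cover of those infusions, text by text.**

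| Infusion | Section 10.5.1 | Cycle tables | Other text |
|---|---|---|---|
| Cycle 1 day 1 | Dexamethasone before | Dexamethasone that day, no order | Synopsis: DHAP after obinutuzumab |
| Cycle 1 day 8 | Dexamethasone before | Silent | 10.1.5 and 10.5.1: prednisolone after a prior reaction |
| Cycle 1 day 15 | Dexamethasone before | Silent | As for day 8 |
| Cycles 2 to 4, day 1 (3 infusions) | Dexamethasone before | Dexamethasone that day, no order | No sentence on order; prednisolone after a prior reaction |

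Read literally, section 10.5.1 covers 6 of 6 infusions. The tables show dexamethasone on the day of 4 of 6 and are silent for 2 of 6 (33%).

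**Order on day 1.** The synopsis sentence is a bullet under Cycle 1. The synopsis block for cycles 2 to 4 and section 10.2.1.2 have no counterpart. The explicit conflict therefore concerns 1 infusion of 6, the first.

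**Effect on reaction rates.** The documents give no rate with or without dexamethasone, so no difference can be computed. For scale only, assume a true grade 4 rate p and count the trigger over n patients. The number needed is the smallest whole number at or above 0.10 × n, which is 7 for n = 70 and 9 for n = 83. The chance of reaching it is P(X ≥ r), with X binomial(n, p):

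| Assumed p | n = 70, r = 7 | n = 83, r = 9 |
|---|---|---|
| 4% | 2.2% | 0.6% |
| 6% | 12.6% | 6.1% |
| 8% | 32.7% | 21.8% |
| 10% | 55.8% | 45.1% |

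The trigger is sensitive to the underlying rate. Nothing in the documents says that steroid timing moves the rate by any of these steps.

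**Primary design.** With X binomial(70, p), P(X ≥ 46) is 0.0452 at p = 0.55 and 0.820 at p = 0.70, and 70 / 0.85 = 82.4, rounded up to 83. These agree with the protocol, and premedication is not an input to any of them.

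**The case against.** The texts can be read as one stepped rule. The tables are headed as chemotherapy regimens and list no premedication at all; the analgesic and antihistamine required by section 10.5.1 are missing from them too. An empty day 8 cell therefore means no DHAP dose that day, not that a steroid is barred. Section 10.5, on prophylactic measures, is the natural home for premedication, and sections 10.1.5 and 10.5.1 refer to each other. On day 1, dexamethasone beforehand with cytarabine and platinum afterwards would fit both texts, and the synopsis phrase about standard premedication might include a steroid. Patients with a prior reaction already have a prednisolone rule.

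Much of this stands, and it rules out four stronger readings that a reader might infer:

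- That the order conflicts on day 1 of all four cycles. The order sentence belongs to cycle 1 only.
- That the tables and section 10.5.1 give opposite instructions for days 8 and 15. The tables are silent, and section 10.1.5 does not say that a steroid is confined to patients who reacted.
- That reaction rates have been shown to depend on which page a site follows. The documents hold no figure for this.
- That SAP Table 7.6-2 must change. The exposure outputs in SAP section 5.9.2 report obinutuzumab alone, so a different dexamethasone row would alter no planned result.

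The objection does not remove the need for harmonising. Its reading has to be assembled by the site: no steroid is named under standard premedication in the synopsis, section 10.5.1 gives no dexamethasone dose for days without DHAP, and no text says whether prednisolone after a reaction replaces dexamethasone or is added to it. Because section 10.5.1 lets premedication lapse only in maintenance, the narrower reading of days 8 and 15 is not secure either.

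**Conclusion.** The point holds as an unreconciled safety instruction. There is a literal conflict of order at one infusion, cycle 1 day 1, if DHAP in the synopsis sentence is taken to include its dexamethasone. Steroid cover is uncertain at two further infusions, cycle 1 days 8 and 15, for patients without a reaction at the prior infusion. Different practice between sites is a possibility that the wording leaves open; the documents do not show that it occurred. The consequence for grade 4 reactions, the IDMC trigger and early discontinuation is plausible but cannot be sized. The sample size and the decision rule are untouched. It should be corrected because the wording governs what sites do at the infusions of an investigational antibody, including the one that the protocol treats as carrying most reactions, and because correction is cheap. No view is taken here on which instruction is right.

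**What to change.** Reconcile section 10.5.1, section 10.1.5, the cycle 1 tables (synopsis and section 10.2.1.1) and the synopsis sentence on the order of DHAP, so that a single premedication statement covers cycle 1 days 1, 8 and 15 and day 1 of cycles 2 to 4. The statement should settle three things: the order of steroid and antibody on day 1, what applies on days without DHAP, and how the rule for patients with a prior reaction relates to the general one. The content is for the sponsor and investigators to choose. The SAP can stay as it is.

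The cost is a wording amendment and a clarification to sites. The protocol planned the last inclusion for September 2018 and SAP version 2.0 is dated October 2024, so induction may already be complete. In that case the useful step is for the study report to say, as far as the records allow, which practice sites followed when it presents infusion reactions.
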